Appendix C: Post-Resuscitation Patient Interview Guide

Post-Resuscitation Patient Interview Guide

Interview to be administered by trained data collectors, responses will not be audio-recorded. Interview to last 10-15 minutes.

Topic areas to cover:

- Experience and understanding of resuscitation (both IV and enteral)
- Palatability of enteral resuscitation
- Prior experience with oral rehydration solution (ORS)
- Challenges with resuscitation (both IV and enteral)
- Positives of resuscitation (both IV and enteral)

Appendix D: Healthcare Worker Focus Group Interview Guides

Focus Group In-Depth Interview Guides

The following templates outline the anticipated questions that will be used in semi-structured focus group interviews with involved healthcare providers. Based on responses, additional probes and questions may be asked to fully explore the responses.

Physician Focus Group

- Have you previously heard of or personally used Oral Rehydration Solution (ORS)?
- How often do you recommend/prescribe ORS in your typical practice?
 - At Nepal Cleft and Burn Center (NCBC)?
 - In other clinical settings?
- What clinical or laboratory datapoints do you use in your practice to diagnose shock?
- What clinical or laboratory datapoints do you find most useful to assess a patient's resuscitation progress?
- What are challenges with implementation of a resuscitation protocol?
 - Thoughts on hourly check of vitals and urine output
 - Thoughts on hourly adjustments to resuscitation volume
- From your participation in this study and observations made, do you think ORS provides an adequate amount of resuscitation?
- Do you think ORS provides an effective method of resuscitation?
- What are advantages to the use of enteral resuscitation in this population?
- What are challenges in the use of enteral resuscitation in this population?
- Do you think it will be beneficial to implement a protocol for resuscitation?
- After participating in this study, will you plan to increase your use of ORS in your clinical practice with burn patients?
- Do you have additional comments, questions, ideas you would like to offer?
-

Nursing Staff Focus Group

- Have you previously heard of or personally used Oral Rehydration Solution (ORS)?
- How often is ORS used for patients with burn injury at NCBC?
- What signs do you typically first notice when a burn patient starts to get sick?
- What are challenges with implementation of a resuscitation protocol?
 - Thoughts on hourly check of vitals and urine output?
 - Thoughts on adjustments to resuscitation volume?
- From your participation in this study and observations made, do you think ORS provides an effective method of resuscitation?
- What are advantages to the use of enteral resuscitation in this population?
- What are barriers in the use of enteral resuscitation in this population?
- What were logistical difficulties with enteral resuscitation?
- Were there differences in children and adult attitudes towards enteral resuscitation?
- After participating in this study, do you think a protocol should be used more often?
 - Should ORS be used more often?
- Do you have additional comments, questions, ideas you would like to offer?

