Patients with electrical and chemical burns will be excluded, as will those with serious inhalation injury requiring treatment to maintain oxygen saturation. Patients in overt shock (defined as serum lactate >2.5 , or hypotension and altered mental status), Pregnant patients, psychiatrically unstable patients will be excluded.

Patients with oropharyngeal defects and/or previously known diagnoses leading to high risk of aspiration, and/or precluding safe nasal-enteric access will be excluded. Patients with history of chronic nausea and/or vomiting, including those with a diagnosis of gastroparesis due to diabetes mellitus will be excluded.

Patients with a Baux score of over 100 (age + TBSA), patients with declared palliative intent on admission, and patients for whom clinicians have high level of clinical concern based on clinical judgement will also be excluded.

Qualitative Component:

Inclusion Criteria

Healthcare workers (physicians, nurses, nursing assistants) who are anticipated to or have provided care to eligible patients in the enteral resuscitation arm of the study.

[figure not shown]
Exclusion Criteria

Exclusion criteria include co-PIs and co-investigators in this study to avoid bias.

11. Intervention

Please see schematic below for Intervention workflow. Specific goal-directed resuscitation protocols for IV fluid resuscitation and Enteral-based resuscitation in **Appendix** including details regarding modifications to allocated interventions based on response, patient request and improving/worsening disease.

Intervention Workflow Overview

General Resuscitation Protocol for Intravenous and Enteral-based Resuscitation

Resuscitation Timeline	Fluid Protocol	Clinical Assessment	Laboratory Assessment*	Additional Interventions
Hour 1	See Appendices A and B	Measure and record vital signs every two hours or more frequently as needed. (Temperature, blood pressure, heart rate, respirations, oxygen saturation), urine output, physical signs of overt shock	CBC, BMP, Lactate, PT/PTT/INR (15 mL)	Additional interventions such as colloid or blood product transfusion, vasoactive agents, escharotomy/ faschiotomy, intubation as deemed necessary by clinical care team will be noted throughout this time period.
Hours 2-7				
Hour 8	Administer Lactated Ringer's (LR) or Oral Rehydration Solution + LR according to calculated Parkland formula**		CBC, BMP, Lactate (10 mL)	
Hours 9-15				

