Hour 16	Add or subtract fluid volume by every 2 hours based on urine output goal of at least 0.5 mL/kg/hr.		CBC, BMP, Lactate (10 mL)	
Hours 16+	IV Metoclopramide to be administered if GI symptoms such as bloating, nausea, discomfort, vomiting.		CBC, BMP, Lactate every 8 hours, and PT/PTT/INR every 24 hours until resuscitation complete.	

* CBC=Complete blood count; BMP=Basic metabolic panel; PT=Prothrombin time; PTT=Partial Thromboplastin time; INR=international normalized ratio

**Parkland formula= $4\text{cc} * \% \text{ Total Body Surface Area burned(TBSA)} * \text{weight(kg)} = 24 \text{ hour fluid volume}$
Total resuscitation volume divided by 2, then divided by 8 to determine the starting resuscitation volume.

12. Outcomes

Goals

The overarching goals are to understand challenges and facilitators of enteral-based resuscitation and understand the effectiveness of the technique compared to standard of care (intravenous resuscitation).

Specific Aim 1: Determine the frequency of adherence to the enteral-based and IV fluid resuscitation protocols, and determine frequency of successful resuscitation.

Hypothesis 1: With goal-directed resuscitation, the primary outcomes of goal average urine output and successful resuscitation will be achieved in the majority of patients (over 50%). Protocol adherence will be at least 50%.

Specific Aim 2: Describe the challenges and facilitators to enteral and IV resuscitation protocol acceptance, implementation, compliance and sustainability.

Hypothesis 2: Enteral resuscitation will have logistical advantages over IV resuscitation, reduce delays in the initiation of resuscitation, have fewer interruptions, and will be easier to implement.

Primary endpoints

For the quantitative aspect, study variables will include measures of implementation and adherence to the enteral resuscitation protocol with variables such as: percent of resuscitation conducted enterally, proportion of protocol laboratory and clinical assessments completed, completeness of bedside documentation, number of inappropriate adjustments of resuscitation fluid rates based on urine output.

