55	20%	2.3	212

15. Recruitment

Patients will be screened by research study team members for eligibility in the Emergency Department at Kirtipur Hospital. All recruitment and screening will occur in the Emergency Department and inpatient setting on admission. No outside recruitment will occur. The study will aim to enroll over the winter season, as this is the timeframe with the highest incidence rate of burn injuries in Nepal.

Methods

16. Allocation

The patient treatment allocation sequence will be generated using the sealed envelope technique. The sealed envelopes for each sequentially numbered enrolled patient (e.g. Patient 1, Patient 2, Patient 3, etc) will contain a pre-assigned intervention arm that will be unknown to the research team prior to each patient's enrollment. Each sealed envelope will only be opened after patient enrollment is complete to reveal patient intervention arm allocation.

17. Blinding

This study is not blinded to the patients or providers.

18. Data Collection Methods

Intervention:

In order to ensure a contextually appropriate intervention and increase engagement, data collection tools have been adapted from the validated Joint Trauma System Burn Care Clinical Practice Guideline 12 (JTS Burn Care CPG 12) burn worksheet and resuscitation flowsheet with feedback from stakeholders at the Nepal Cleft and Burn Center. Please see attached documents (Resuscitation Flowchart and Documentation Chart) for the latest versions developed by the research and clinician team, to be further adapted for ease of use as needed.

Clinical data pertaining to the resuscitation interventions will be collected and documented by the bedside nurses and clinicians on the adapted Documentation Chart, with documentation of i) brief history and physical exam ii) two-hourly assessments of vitals, intake, output, and symptoms and iii) 8 hourly laboratory test results. This data will subsequently be transcribed into a secure electronic format by research assistants utilizing the RedCAP data collection system.

Post-resuscitation patient interview answers will be recorded on the RedCAP data collection system.

Qualitative Component:

Data collection tools include focus group interview guide which will serve to guide the semi-structured 1-hour discussions pre-enrollment, at 50% enrollment and after completion of enrollment with groups of doctors and nurses caring for the patients enrolled in the study. The

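### The healthcare-worker focus groups give no matched provider view of the IV protocol, although Aim 2 covers both protocols and Hypothesis 2 compares them

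*Combined protocol and SAP*

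**What the plan says.** Section 12 states Specific Aim 2 for both protocols: "Describe the challenges and facilitators to enteral and IV resuscitation protocol acceptance, implementation, compliance and sustainability". Hypothesis 2 is directional: "Enteral resuscitation will have logistical advantages over IV resuscitation, reduce delays in the initiation of resuscitation, have fewer interruptions", and it adds that enteral resuscitation will be easier to implement.

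Two sections describe who joins the focus groups, and they differ. Section 10 (Qualitative Component) admits healthcare workers "who are anticipated to or have provided care to eligible patients in the enteral resuscitation arm of the study". Section 18 describes discussions "with groups of doctors and nurses caring for the patients enrolled in the study", with no restriction by arm. Section 18 schedules the 1-hour discussions before enrollment, at 50% enrollment and after enrollment ends.

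Appendix D gives one guide for physicians and one for nursing staff. Both ask "What are advantages to the use of enteral resuscitation in this population". The nursing guide adds "What were logistical difficulties with enteral resuscitation". Both also ask a question that names no route: "What are challenges with implementation of a resuscitation protocol". The introduction to Appendix D allows further probes and questions depending on the answers given.

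Three other parts of the plan bear on Aim 2. The patient interview in Appendix C covers experience, challenges and positives for both routes. Section 20 puts patient and focus-group interviews into the same template analysis. The Documentation Chart in Appendix B records resuscitation start time, time since injury, and planned and given fluids every two hours, with separate oral and IV columns.

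**The concern.** A claim that one route is easier to implement than another needs accounts of both, preferably from the same people in answer to the same questions. A template analysis organizes what the interviews elicit. If providers are prompted for the advantages, difficulties and effectiveness of enteral resuscitation but never for those of IV, the coded material will be rich on one route and incidental on the other. Any IV content would then depend on who happens to raise it.

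Providers matter here because section 12 lists burden on healthcare workers and their comfort with the protocol among the qualitative variables, and says these variables will be drawn from the interview guides. The background text before section 7 also names the feasibility of protocolized IV resuscitation as a gap that the project addresses. At stake is whether the trial can report a provider-side comparison for its own Hypothesis 2, or only a list of enteral facilitators and barriers. Provider views not collected at a given round cannot be recovered later.

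**Working it through.** No calculation applies; the check is a reading of the aim, the hypothesis, the eligibility rule and the instruments side by side.

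**Step 1. Scope of the aim.** Aim 2 names both protocols. Hypothesis 2 has four parts, each comparing enteral with IV: logistical advantage, delay to initiation, interruptions, and ease of implementation.

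**Step 2. Route-specific questions in Appendix D** (adequacy, effectiveness, advantages, challenges or barriers, logistics).

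| Topic | Physician guide | Nursing guide | IV counterpart |
|---|---|---|---|
| Adequacy | ORS | not asked | none |
| Effectiveness | ORS | ORS | none |
| Advantages | enteral | enteral | none |
| Challenges or barriers | enteral | enteral | none |
| Logistical difficulties | not asked | enteral | none |
| Count | 4 | 4 | 0 |

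Neither guide contains the term IV or intravenous.

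**Step 3. Route-neutral questions.** Both guides ask about challenges of implementing a protocol, with prompts on checking vitals and urine output and on adjusting volume. The physician guide asks whether a protocol would be beneficial, and the nursing guide asks whether one should be used more often. Both arms are protocolized and share the monitoring and adjustment steps. These questions can therefore draw answers about IV, but mainly on the burden of having a protocol. They do not separate one route from the other, which is what Hypothesis 2 is about.

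**Step 4. Recruitment.** Section 10 qualifies staff by "care to eligible patients in the enteral resuscitation arm of the study". Section 18 has no arm limit. Read literally, someone who cared only for IV-arm patients fits section 18 but not section 10.

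**Step 5. What other sources supply for each part of Hypothesis 2.**

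| Part of Hypothesis 2 | Source covering both arms | What is missing |
|---|---|---|
| Delay to initiation | Chart: start time, time since injury | No specific analysis written |
| Interruptions | Chart: planned versus given fluids, which may allow it | No definition or analysis written |
| Logistical advantage | Patient interviews, from the patient's side | Provider account of IV |
| Ease of implementation | None that measures it from the provider's side | Provider account of IV |

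Section 20 promises descriptive and comparative statistics on implementation metrics but does not assign a data source to any part of Hypothesis 2.

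**Result.** The gap falls on the last two rows and is confined to healthcare-worker evidence.

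**The case against.** The strongest reply is that the plan has more on IV than the guides suggest, and most of that reply stands.

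- *Patient interviews.* They cover both routes explicitly and enter the same template analysis. A reader might infer that the whole Aim 2 comparison is one-sided; the documents do not support that. Patients cannot, however, report on staff workload or ease of implementation.
- *Route-neutral questions and probes.* A reader might infer that the guides ask nothing that bears on IV. That is too strong: several questions name no route, and the guides are semi-structured. The accurate statement is that neither guide names IV. The probes depend on earlier answers, and none is scripted for IV.
- *Implied comparator.* Asking for the advantages of enteral resuscitation invites a comparison with the standard of care. It may do so, but it does not ask for the advantages or difficulties of IV itself.
- *Recruitment.* Section 10 is an inclusion rule and does not bar staff who also treat IV-arm patients. At a single center overlap is plausible, though not stated. Section 11 pairs ORS with Lactated Ringer's and Appendix B includes IV boluses, so enteral-arm staff may also handle IV fluid. Even so, these staff are not asked about the IV protocol.
- *Chart data.* Delay, and perhaps interruptions, could be compared without focus groups. A reader might infer that Hypothesis 2 as a whole could be neither supported nor refuted; the chart data show otherwise.
- *Preference.* Strict mirroring of every question is one choice among several, and a smaller set of paired questions could do. This stands and shapes the fix.

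**Conclusion.** The point holds in a limited form. As scripted, the focus groups yield no matched provider account of the IV protocol: four enteral or ORS questions per guide on the topics that matter, and no IV counterpart. Section 10 ties eligibility to the enteral arm, which does not agree with section 18. The consequence is confined to the provider view of IV, chiefly the logistics and ease-of-implementation parts of Hypothesis 2. Aim 2 is otherwise partly covered by the patient interviews, the route-neutral questions and the charts.

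This rests on the guides being used broadly as written. A moderator who probed IV consistently would narrow the gap, but nothing in the plan requires it. Only one guide per staff group is supplied for the three rounds, so the gap would probably recur. It would not recur identically, because some questions presuppose participation and cannot be asked as worded before enrollment.

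This is a cheap improvement. It does not affect randomization, treatment or the quantitative sample size.

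**What to change.** 1. In Appendix D, add IV counterparts to the questions on advantages, on challenges or barriers, and (in the nursing guide) on logistical difficulties.
2. Add to both guides one direct enteral-versus-IV question covering starting resuscitation, interruptions and workload.
3. Align the qualitative eligibility criterion in section 10 with section 18, so that staff caring for patients in either arm qualify.
4. Optionally, add a line to section 20 saying which data source addresses each part of Hypothesis 2.

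The cost is a guide revision, a small change to the eligibility wording, and a few added minutes in each 1-hour session.
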